ALZUMAB™ should not be administered to patients having history of severe allergy or known hypersensitivity reaction to any component of ALZUMAB™ or any murine proteins. Additionally, ALZUMAB™ is contraindicated in patients with any active serious infection including tuberculosis and HIV-AIDS.

It is recommended that live/attenuated vaccines not be given concurrently with ALZUMAB™.

As with other IgG antibodies, itolizumab may cross the placenta during pregnancy. The available clinical experience is too limited to exclude a risk, and administration of ALZUMAB™ is therefore not recommended during pregnancy.

Infections and Reactivation of Tuberculosis

Physicians should exercise caution before and during Itolizumab Injection treatment in patients with a history of recurrent infections or underlying conditions which may predispose them to serious infections. Patients should be monitored closely for the development of signs and symptoms of infection during and after treatment with Itolizumab.

4. Objectives

Primary Objectives:

To study the efficacy and safety of adding Itolizumab in patients with Moderate to Severe COVID-19 complications (Cytokine Release Syndrome).

Secondary Objectives:

To study the effect of immunomodulation by Itolizumab and its correlation to clinical improvement by evaluating biomarker data (IL6, TNF-a, IL17, IL1, Interferon -A etc.) before and after Itolizumab treatment

5. Outcome Measures

Primary Outcome Measures:

1. Proportion of patients with deterioration of lung function as measured by*:
 - Stable SpO₂ without increasing FiO₂
 - Stable PaO₂ without increasing FiO₂
2. Reduction of endo-tracheal intubation rate, measured as rate of patients needing intubation*
3. Reduction in proportion of patients who need*
 - Non-invasive ventilation
 - Invasive mechanical ventilation
 - High flow nasal oxygen
4. Time of duration of mechanical ventilation or time to end of mechanical, measured as elapsed time from the start date of mechanical ventilation to the weaning date, for patients needing intubation*
5. One-month mortality rate between the two arms* [Time Frame: up to 1 month]

1-month mortality is defined as the ratio of patients who will live after 1month from study start out of those registered at baseline

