6. Change in inflammatory markers like CRP (C-reactive protein) level, d-Dimer, ferritin etc. [Time Frame: Arm A; baseline, during treatment (Before every dose and 12 to 24 h after every dose) up to 1 month, Arm B: baseline, 12 to 24 h and approx. 7 and 14 days after randomization]

Secondary Outcome Measures:

1. Biomarkers (IL-6, TNF-a, IL1, IL17, etc...) [Time Frame: Arm A; baseline, during treatment (Before every dose and 12 to 24 h post dose) up to 1 month, Arm B; baseline, 12 to 24 h and approx. 7 and 14 days after randomization]
2. Lymphocyte count [Time Frame: Arm A; baseline and before every dose up to 1 month, Arm B; baseline, approx. 7 and 14 days after randomization]
Lymphocyte count assessed by routinely used determination of blood count
3. PaO₂ (partial pressure of oxygen) / FiO₂ (fraction of inspired oxygen, FiO₂) ratio (or P/F ratio) [Time Frame: Arm A; baseline, during treatment (Before every dose and 48 h post dose) up to 1 month, Arm B: baseline, 48 h and approx. 7 and 14 days after randomization]
calculated from arterial blood gas analyses (values from 300 to 100)
4. Number of participants with treatment-related side effects as assessed by Common Terminology Criteria for Adverse Event (CTCAE) version 5.0 [Time Frame: during treatment and up to 30 days after the last treatment dose]*
graded according to CTCAE criteria (v5.0)
5. Radiological response [Time Frame: at baseline, after seven days and if clinically indicated (up to 1 month)]*
Thoracic CT scan or Chest XR
6. Duration of hospitalization [Time Frame: from baseline up to patient's discharge (up to 1 month)]*
Days of hospitalization and ICU
7. Remission of respiratory symptoms [Time Frame: up to 1 month]*
time to independence from non-invasive mechanical ventilation calculated in days
8. Remission of respiratory symptoms [Time Frame: up to 1 month]*
time to independence from oxygen therapy in days

* Applicable for both arms

6. Population

Patients who have tested positive for virological diagnosis of SARS-CoV2 infection (PCR) are planned to be randomised for enrolment from various centres in India.

Inclusion Criteria:

1. Male or female adults above 18 years (not tested in children yet)
2. Informed consent for participation in the study
3. Confirmed virological diagnosis of SARS-CoV2 infection (RT-PCR)
4. Hospitalized due to clinical worsening of COVID-19 infection
5. Oxygen saturation at rest in ambient air $\leq 94\%$

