6. Patients who are in moderate to severe ARDS as defined by PaO₂/Fio₂ ratio of < 200 or more than 25% deterioration from the immediate previous value.
7. Baseline serum ferritin level ≥ 400 ng/mL or IL-6 levels greater than 4 times ULN, if known

Note: Either of Inclusion number 6 or 7 is required for inclusion of the patient into the study. Since there is logistical delay in getting results in time, biomarker data as inclusion criteria may be used if already known.

Exclusion Criteria:

1. Known severe allergic reactions to monoclonal antibodies
2. Active tuberculosis (TB) infection
3. History of inadequately treated tuberculosis or latent tuberculosis

Note: Latent tuberculosis should be excluded based on history, physical examination and chest x ray before dosing (day 1). QuantiFERON TB also should be performed, however considering criticality of patient condition, patient can be dosed without QuantiFERON TB test results. If QuantiFERON TB test is positive, then continuation of patient in the study is investigator's discretion considering benefit-risk evaluation with the sponsor.

4. In the opinion of the investigator, progression to death is highly probable, irrespective of the provision of treatments
5. Patient on invasive mechanical ventilator support.

6. Have received oral anti-rejection or immune-suppressive drugs within the past 6 months

Note: Patient receiving oral anti-rejection or immune-suppressive drugs regularly in the last 6 months will be excluded. Patient will be included if received short course of steroids.

7. Participating in other drug clinical trials like using anti-IL-6 therapy like tocilizumab (participation in COVID-19 anti-viral trials may be permitted if approved by Sponsor)
8. Patient on treatment of anti-IL-6 or plasma therapy as a part of supportive care

9. Pregnant or breastfeeding, or positive pregnancy test in a pre-dose examination
10. Any serious medical condition or abnormality of clinical laboratory tests that, in the investigator's judgment, precludes the patient's safe participation in and completion of the study
11. Patients with known history of Hepatitis B, Hepatitis C or HIV
12. Absolute Neutrophils count (ANC) $<1000 / \text{mm}^3$
13. Platelet count $<50,000 / \text{mm}^3$
14. Absolute Lymphocyte count (ALC): $<500/\text{mm}^3$

Note: ANC, ALC and platelet counts can be done in local lab in the hospital.

Planned number of subjects:

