Approximately 30 patients are considered sufficient to explore the study objectives and will be included in this study (number of patients may be increased if there is benefit observed in initial cohort of patients. There is no formal sample size calculation estimated).

Method of assigning patient to treatment group:

All eligible patients entering into the study will be randomized in 2:1 ratio to receive the treatment A/ B respectively. A computer derived randomization schedule is planned to be generated using appropriate system e.g. SAS to assign patient to treatment groups. Randomization will be central and appropriate system (e.g. remote telephone based, computer-based email, sealed envelope) will be used to distribute randomization schedule to the site

Note: If the patient is randomised to Arm A and is not initiated itolizumab or not administer one full infusion, is then not considered randomized. The same randomisation code will be used for the subsequent subject in that particular site.

Approximate number of sites:

1-10 sites

7. Treatment

Treatment Intervention and Dose:

Arm A: Best supportive care + Itolizumab

The best supportive care to be given as per the institutions protocol will be administered

(e.g: antivirals /antibiotics/ hydroxychloroquine; oxygen therapy, etc) + **Itolizumab**

Itolizumab

Note: Premedication: Hydrocortisone 100 mg i.v (or equivalent short acting glucocorticoid) and Pheniramine 30 mg per i.v. about 30 ± 10 minutes prior to infusion.

Start at 1.6 mg/kg dose iv infusion, if well tolerated, investigator has the discretion to continue with 1.6 mg/kg dose every 2 weeks or 0.8 mg/kg weekly regimen.

Subsequent dose and frequency can be modified, deferred or stopped if patient recovers as per investigator's discretion. If patients' overall parameters improve (if performed and RT-PCR is negative) further dose need not be given. Total infusion received during study duration can vary from 1 to 4 for each patient.

Arm B: Best supportive care

The best supportive care to be given as per the institutions protocol will be administered

(e.g: antivirals/antibiotics/ hydroxychloroquine; oxygen therapy, etc)

Dosing, Handling and Storage of Itolizumab

- Itolizumab is to be stored in 6R, USP type-1, 10 mL glass vials, refrigerated condition at 2°C to 8°C and is stable at that temperature for 36 months.

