For the evaluation of safety, all the evidences of adverse events occurring during the study will be considered. The clinical laboratory tests will be conducted at local labs as and when necessary for safety evaluation. Any investigation, at any time during the study may be conducted at the local lab as per investigator's discretion, in order to monitor safety. Definitions of adverse events and safety reporting for SAEs and SUSARs will be as per regulatory requirements for marketed products (Refer Appendix 3 for details on definitions and reporting that Investigators must follow to satisfy regulatory requirements and ensure patient safety and well-being).

Special Precautions

In general, according to previous data, ALZUMAbTM is safe and well tolerated. However, it is recommended that investigators should exercise caution before administering ALZUMAbTM in subjects with a history of recurrent infections, or underlying conditions which may predispose them to infections. Subjects who develop a new infection while undergoing treatment with ALZUMAbTM should be monitored closely and treated according to standard treatment guidelines. While previous clinical study data has not revealed the incidence of opportunistic infections, it is recommended that Investigators be watchful for occurrence of tuberculosis and opportunistic infections like candidiasis. Administration of ALZUMAbTM should be discontinued if a subject develops a serious infection (other than COVID19). In case a reactivation of latent tuberculosis occurs in study subjects during the clinical study, immediate treatment in accordance with standard medical practice should be instituted and the subjects should be withdrawn from the study.

10.Data Handling Procedures

Source Documents

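### Exclusion 1 is narrower than the protocol's own hypersensitivity contraindication, and active serious infection other than TB, HBV, HCV or HIV is kept out at entry mainly by investigator judgement

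*Protocol*

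**What the plan says.** **Contraindications.** Protocol Section 3 (Summary of Contraindications/warning) rules out dosing in patients with a "history of severe allergy or known hypersensitivity reaction to any component of" the product, or to any murine protein. It adds that the drug "is contraindicated in patients with any active serious infection including tuberculosis and HIV-AIDS". The Contraindications section of the package insert (Appendix 4) repeats the hypersensitivity bar and the bar on any active serious infection.

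**Entry criteria.** Protocol Section 6 lists 14 exclusions, and SAP 4.4 repeats them. Exclusion 1 is "Known severe allergic reactions to monoclonal antibodies". Exclusions 2 and 3 cover tuberculosis; Exclusion 11 covers known hepatitis B, hepatitis C or HIV. Exclusion 10 opens with "Any serious medical condition or abnormality of clinical laboratory tests" and applies where the investigator judges that safe participation is precluded. Exclusion 4, also a matter of opinion, applies where "progression to death is highly probable, irrespective of the provision of treatments".

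**Randomisation.** Section 6 states: "All eligible patients entering into the study will be randomized in 2:1 ratio". A note there, repeated in SAP 4.5, says an Arm A patient who does not start itolizumab, or does not complete one full infusion, is not counted as randomised, and the code passes to the next subject at that site.

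**On study.** Section 9 (Special Precautions) says the drug "should be discontinued if a subject develops a serious infection (other than COVID19").

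**The concern.** The listed criteria are the check that sites carry out and record. Footnote a to the schedule in Section 8.1 has all of them reviewed before first dosing, and randomisation depends on eligibility. The dosing text in Section 7 does not refer back to the Section 3 contraindications. A contraindication that appears only in the Background or the package insert is therefore outside the documented entry check.

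At stake is the safety of an affected patient. Someone with a known excipient hypersensitivity, say, can pass Exclusion 1 and be randomised. On allocation to Arm A the site has two choices: infuse against Section 3, or withhold the drug and replace the patient under the Section 6 note. Checking the contraindication before randomisation avoids both.

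The infection rules are also uneven. A serious non-COVID infection that arises on study stops the drug under a stated rule. The same infection present at screening is not a named bar to entry.

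**Working it through.** There is no figure in the plan to reproduce and no arithmetic applies. The check sets Section 3 against the exclusions in Section 6 (identical in SAP 4.4).

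| Section 3 bars dosing in | Entry criterion that reaches it | What is left |
|---|---|---|
| Severe allergy to itolizumab itself | Exclusion 1, since itolizumab is a monoclonal antibody | Nothing |
| Known but non-severe hypersensitivity to itolizumab | None named | Not covered by Exclusion 1 |
| Hypersensitivity to another component; Appendix 4 lists polysorbate 80 among the excipients | None named | Not covered by Exclusion 1 |
| Hypersensitivity to a murine protein | Exclusion 1, only for a severe reaction to a murine antibody | All other murine-protein hypersensitivity |
| Tuberculosis | Exclusions 2 and 3 | Named; a positive QuantiFERON result after dosing is left to discretion |
| HIV-AIDS | Exclusion 11 | Named |
| Any other active serious infection | Exclusion 10 by judgement; Exclusion 4 by judgement if death is thought highly probable; Exclusions 5, 12, 13 and 14 incidentally (invasive ventilation, blood counts) | Not named |

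Three points follow.

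1. *Hypersensitivity.* Exclusion 1 and Section 3 overlap, but neither contains the other. Exclusion 1 is wider in one respect, because a severe reaction to any monoclonal antibody excludes. It is narrower in the three respects shown. Here a stated entry rule is looser than the protocol's own dosing rule.

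2. *Infection.* In Section 3, tuberculosis and HIV-AIDS are introduced as included cases, so they are examples and not the whole list. The exclusions name those examples, add hepatitis B and C, and leave the general category to judgement.

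3. *COVID-19.* Section 3 has no exception for COVID-19, while Inclusion 4 requires patients to be "Hospitalized due to clinical worsening of COVID-19 infection". The infection contraindication therefore cannot be copied word for word into Section 6. The exception it needs already exists in Section 9, but only for infections that develop on study.

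**The case against.** The strongest reply concerns infection. Exclusion 10 is a numbered criterion, an active serious infection is a serious medical condition, and Section 3 tells the same investigator that the drug is contraindicated in it. In substance, such a patient should already be excluded. This largely stands: what an added criterion gains is explicitness and consistency across up to 10 sites, since deciding what counts as serious needs judgement under either wording. It does not explain why tuberculosis, hepatitis and HIV were named when the rest of the same contraindication was not.

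The reply is weaker for hypersensitivity. A past non-severe reaction or an excipient allergy is not obviously a serious medical condition, so Exclusion 10 is a less natural route. Premedication with hydrocortisone and pheniramine, infusion over at least 120 minutes (Section 7) and the infusion-reaction guidance in Appendix 3 lower the risk during dosing. They do not make a contraindicated patient eligible for the drug.

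A reader might infer that the contraindications are missing from the protocol. They are not: Section 3 and Appendix 4 both bar dosing. A reader might also infer from the absent COVID-19 exception that Section 3 forbids treating every trial patient. Section 9 shows that this is not the intended meaning. Finally, the package insert says the drug has not been studied in active intercurrent infection, but that applies to every patient with COVID-19 and does not isolate the added risk of a second infection.

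**Conclusion.** The mismatch is real and can be read directly from the text. It is a cheap improvement to patient safety, minor to moderate in size. It is firmest for Exclusion 1, where the entry rule is narrower than the contraindication. For infection it is a matter of making explicit what Exclusion 10 already reaches by judgement.

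The conclusion assumes that sites apply the Section 6 list as the entry check and that the Section 3 contraindications are meant to hold in this trial, apart from COVID-19 itself. The documents do not say how many patients would be affected, and no number is assumed.

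A reader might go further and infer a distorted comparison between arms, because an undosed Arm A patient is replaced. Any such effect would come from the replacement rule, which is a separate matter, and would depend on an unknown number of patients. No effect on endpoints or analysis is claimed here.

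**What to change.** - Reword Exclusion 1 to bar: *previous severe allergy to, or known hypersensitivity of any grade to, itolizumab, any of its excipients or any murine protein; or a severe allergic reaction to any monoclonal antibody*. This keeps the part of the present criterion that is wider than Section 3.
- Add an exclusion: *known or clinically suspected active serious infection other than COVID-19, in the investigator's assessment of the screening data*. This brings the Section 9 exception to the point of entry.
- Make the same changes in SAP 4.4.

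The new criterion should rest on clinical assessment, not on proof of infection. The schedule in Section 8.1 provides history, examination, chest imaging, haematology and biochemistry including procalcitonin, but no cultures. Imaging will also be hard to read in patients who already have COVID-19 lung disease. It would be too much to say that the scheduled tests settle the question, but the wording above does not require a new one.

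The cost is two edits in each document and a few otherwise eligible patients not enrolled. Their number is unknown. *Serious* still needs clinical judgement.

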8.1 Schedule of Study Visits and Procedures

Visit	S1	W1	W2	W3	W4	End of Study
Weeks	-2 to 0	0	1	2	3	4 th week
Days	-14	1 [^]	8 [^]	15 [^]	22 [^]	30 [#]
Event						
Informed Consent	X					
Medical History	X					
Inclusion/Exclusion Criteria ^a	X					
Weight	X	X	X	X	X	X
Physical Examination, Vital signs ^{\$}	X	X	X	X	X	X
Hematology* [;] ^{\$}	X	X	X	X	X	X
Biochemistry** [;] ^{\$}	X	X	X	X	X	X
Chest X Ray/CT scan ##	X	X	X	X	X	
Randomisation	X					
Best Supportive Care		X	X	X	X	
Pre-medication @ in Arm A		X	X	X	X	
ALZUMAb infusion ^b		X	X	X	X	
Cytokines and Immunophenotyping assessment	X	X ^d				
PaO ₂ /FiO ₂ ratio	X	X	X	X	X	
CRP	X	X	X	X	X	X
Daily Morning SOFA Score ^c	X	X	X	X	X	
Concomitant medication check	X	X	X	X	X	X
Adverse events	X	X	X	X	X	X

[^] Window period: ± 48 Hours.

^a All inclusion / Exclusion criteria to be reviewed prior to first dosing. Screening period is up to 14 days however screening and baseline visit can happen in one day and screening assessment can be considered as baseline assessments.

^b 1.6 mg/kg dose iv infusion, if well tolerated and improvement in patient observed, investigator has the discretion to continue with 1.6 mg/kg dose every 2 weeks or 0.8 mg/kg weekly regimen in combination therapy with standard of care (anti-viral and antibiotic drugs). Subsequent dose and frequency can be modified, deferred or stopped if patient recovers as per investigator's

discretion. If patients' overall parameters improve (if performed and RT-PCR is negative) further dose need not be given. Total infusion received during study duration can vary from 1 to 4 for each patient. If patient recovers/is discharged earlier than 30 days, then patient should be contacted telephonically to get status of the patient on 30th day after enrolment.

c: Daily SOFA Scoring until patient moved out of ICU/equivalent, and later SOFA score frequency as per investigator discretion. If patient is not admitted in the ICU/equivalent at the time of enrolment, then it is recommended to capture these assessments daily for first 7 days.

Window period for assessment at 4th week or 30th day is \pm 3 days.

*Hematology assessments (blood test) include: hemoglobin, total leukocyte count, differential count, absolute neutrophil count, absolute lymphocyte count, and platelet count.

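### In this open-label trial, reuse of an undosed Arm A code makes the next allocation at that site known in advance, and nothing in the plan locks eligibility before the arm is known

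*Protocol*

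**What the plan says.** **Allocation.** Protocol section 6 (method of assigning patients), repeated in SAP 4.5, states: "Randomization will be central and appropriate system (e.g. remote telephone based, computer-based email, sealed envelope"), and that this system "will be used to distribute randomization schedule to the site". Neither document says that one assignment is released per patient after eligibility has been confirmed, or that the site holds no list.

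**Undosed Arm A patients.** A note in the same paragraph says that a patient assigned to Arm A who does not start itolizumab, or does not receive one full infusion, does not count as randomised. It continues: "The same randomisation code will be used for the subsequent subject in that particular site". There is no matching rule for Arm B.

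**Analysis sets.** SAP 7 defines ITT/FAS as everyone randomised in Arm B, but in Arm A only those who received at least one full dose. The note under SAP table 14.1.1 (screening failures) has a place to report how many patients were replaced for this reason.

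**Eligibility.** Section 6 says: "All eligible patients entering into the study will be randomized in 2:1 ratio". The visit table in protocol 8.1 marks eligibility and randomisation once each, both in the screening column, with the first infusion on Day 1. Footnote a adds: "All inclusion / Exclusion criteria to be reviewed prior to first dosing", and "Screening period is up to 14 days however screening and baseline visit can happen in one day". Exclusion 4 reads: "In the opinion of the investigator, progression to death is highly probable, irrespective of the provision of treatments". Exclusion 10 also rests on the investigator's judgement.

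**Blinding.** SAP 4.1 describes the trial as open label.

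**The concern.** A fair comparison needs two things: nobody can foresee the next arm while deciding whether to enrol a patient, and nobody leaves the comparison because of what happened after the arm was known. The reuse rule breaks the first for one patient each time it operates. The rule on randomised status, carried into the ITT/FAS definition, breaks the second in Arm A only.

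The wording on distribution of the schedule and on the timing of eligibility review leaves the way open for more. Exclusions 4 and 10 are judgements about prognosis and fitness. If they can be applied while the arm is known, a very sick patient assigned to itolizumab can be dropped and replaced, while a similar patient assigned to best supportive care stays in. One-month mortality, intubation and ventilation are all primary outcomes, so the selection would act directly on them and would favour Arm A.

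**Working it through.** The plan gives no event rate, effect size or power figure, so there is no stated number to reproduce. The check has two parts.

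**1. What the rules do when followed as written**

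- Before any reuse, the 2:1 ratio gives the next patient a 2/3 = 67% chance of Arm A. After an undosed Arm A patient, the next patient at that site has a 100% chance. This holds even if central release is otherwise perfect.
- An Arm A patient who dies, deteriorates or is judged unsuitable between assignment and the end of the first infusion leaves the randomised set. An Arm B patient with the same course stays. The interval can be anything from the same day to 14 days (protocol 8.1, footnote a).
- SAP 8 takes baseline as the last value before study drug in Arm A but before randomisation in Arm B, so the plan itself treats the two moments as distinct.

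**2. How large the bias could be**

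Inputs from the documents: about 30 patients at 2:1, which is 30 × 2/3 = 20 in Arm A and 30 × 1/3 = 10 in Arm B; two-sided 5% tests.

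Assumptions, not in the documents: true one-month mortality *p*, the same in both arms; a share *q* of Arm A patients who would die is screened out before dosing and replaced from the same population under the same screening; Arm B is untouched. The SAP names no test for the mortality difference, so the pooled z test and Fisher's exact test were both evaluated by exact binomial enumeration.

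Observed Arm A mortality is then

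pA = p(1 − q) / [p(1 − q) + (1 − p)].

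At p = 20% and q = 50%: 0.10 / (0.10 + 0.80) = 11.1%, against 20% in Arm B, a spurious difference of −8.9 points.

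| q (p = 20%) | Arm A mortality | Difference, points | False benefit, z test | False benefit, Fisher |
|---|---|---|---|---|
| 0 | 20.0% | 0 | 2.7% | 1.8% |
| 10% | 18.4% | −1.6 | 3.5% | 2.3% |
| 25% | 15.8% | −4.2 | 5.1% | 3.5% |
| 50% | 11.1% | −8.9 | 10.5% | about 7% |

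False benefit is the probability of a significant result in favour of Arm A when the drug does nothing.

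Over p = 10% to 40%:

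- q = 0: z 2.7% to 3.6%; Fisher 1.3% to 1.9%.
- q = 25%: difference −2.3 to −6.7 points; z 5.1% to 6.1%; Fisher 1.9% to 4.1%.
- q = 50%: difference −4.7 to −15.0 points; z 9.5% to 14.4%; Fisher 2.9% to 10.8%.

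Few patients are needed. At p = 20% and q = 50%, a fraction 0.20 × 0.50 = 0.10 is removed, so filling 20 places takes 20 / 0.90 = 22.2 patients, or about 2.2 removals. Each removal of a certain death, replaced by a patient with 20% risk, shifts Arm A by (1 − 0.20) / 20 = 4 points, and 2.2 × 4 is about 8.9, which agrees with the table.

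**The case against.** The strongest reply is that much of this is loose wording. The sentence opens by calling randomisation central, and telephone, e-mail and sealed envelopes are ordinary ways to issue single assignments; sealed envelopes are themselves a concealment device. Section 6 randomises eligible patients, which puts eligibility first. Exclusions 4 and 10 are entry criteria, and no text directs that they be applied once the arm is known. Code reuse affects one patient at one site at a time, only after an undosed Arm A case, and reveals nothing about an upcoming Arm B slot.

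These points stand and they limit the claim. A reader might infer four stronger things that the documents do not support:

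- **That sites hold an open list.** The text is ambiguous and may mean single assignments.
- **That eligibility is reviewed a second time after randomisation.** Footnote a says only that review precedes first dosing, and the table marks eligibility once, beside randomisation. The two may fall on one day.
- **That two steered patients create a false difference of 10 to 20 points.** This comes from 2 × 1/20 = 10 and 2 × 1/10 = 20. It treats both patients as certain events and ignores replacement, and the upper end needs sight of upcoming Arm B slots.
- **That no analysis could repair the bias.** This is true of selection before allocation. Removal after allocation is repaired by following everyone and analysing them as randomised.

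The reply does not reach the reuse rule, the Arm A-only rule on randomised status, or the matching ITT/FAS definition. Those are explicit.

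**Conclusion.** The point holds in this form. Following the plan exactly, the patient after each undosed or incompletely dosed Arm A patient at a site has a known allocation, and such patients leave the comparison in Arm A only. In addition, no text requires eligibility to be settled before the arm is known, so opinion-based exclusions could be applied with that knowledge. The documents permit this; they do not show that it happened or was intended.

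The direction of the resulting bias favours Arm A if the patients removed are at higher risk than those who replace them. Its size cannot be fixed from the documents. With 20% mortality, no drug effect and half of would-be Arm A deaths screened out, Arm A shows about 11% against 20%; with a quarter screened out, about 16% against 20%. The mortality and the screening shares are assumptions, and with weak selection the bias is a point or two.

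**What to change.** In protocol section 6 and SAP 4.5, replace the distribution sentence and the reuse note with these rules:

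1. Eligibility is confirmed and the form locked before an assignment is requested.
2. The central service then releases one assignment for that patient, by telephone or e-mail.
3. No list or envelopes are held at site.
4. A code is never reused. If more dosed patients are wanted, new codes are added.
5. A patient who is not dosed, or not fully dosed, keeps randomised status, is followed to Day 30, and is analysed in the assigned arm.

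In protocol 8.1 footnote a, state that any pre-dose check does not alter randomised status. This leaves the decision whether to dose untouched.

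In SAP 7, define ITT/FAS as all randomised patients in both arms; the safety population can still depend on exposure. In SAP 14.1.1, remove the replacement note and report undosed and incompletely dosed patients in the disposition table by arm. If any codes have already been reused, list those cases by site with the reason and the survival status.

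The cost is an amendment to both documents, a short wait per allocation, and some undosed patients in the Arm A analysis set, which may dilute a true effect. Telephone and e-mail release are already named as options.
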